a repeat induction of BCG for patients with disease refractory to the first BCG induction only has a response rate of around 20%. Cystectomy is offered to patients who have high risk NMIBC and those who may be resistant to BCG. However, few patients want to undergo such a radical surgery. Improvements in BCG treatment, particularly the addition of systemic immunotherapy may lead to improved response rates, decreased rates of recurrence and better survival without the need for cystectomy.

Patients undergoing BCG therapy must be able to tolerate induction therapy. For any strategy to improve the anti-cancer efficacy of intravesical BCG completion of induction therapy is required. This study includes a safety lead-in to ensure patients tolerate the combination therapy of full dose BCG and a novel weekly dosing of avelumab. BCG has been shown to be effective in split dosing. If patients are not tolerant of full dose BCG, reduced dosing will be evaluated. For this study to proceed, patients must be able to tolerate induction therapy as commonly defined as receiving at least 5 of 6 weekly treatments within an 8 week period. The completion of a full induction course within eight weeks of starting treatment is the primary endpoint of this study. Patients who cannot tolerate 5 of 6 weekly treatments as part of induction therapy will be considered treatment failures.

The response to treatment at the 6 month mark has been shown to be predictive of further tumor recurrence [11]. A secondary endpoint of this study will be the rate of completion of the 6 month maintenance course which will simultaneously evaluate for tolerance of therapy at 6 months and disease response. This measure will provide a clinically meaningful endpoint of both safety and efficacy.

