5.2.1 Definition of Dose limiting toxicity

During safety lead-in phase, Dose limiting toxicity (DLT) will be monitored during the first 6 weeks of the combination avelumab and intravesical BCG. DLTs will be defined as any and all adverse events at least possibly related to study drug which occur in the DLT evaluation period and meet the criteria below, as evaluated by the NCI-CTCAE version 5.0.

Note: DLTs and other toxicities will be discussed between the Principal Investigator, and the Data Safety Monitoring Committee (DSMC). The discussions are the basis for the decisions regarding dose expansion (or de-escalation) according to the rules of the protocol.

DLT will be classified as either hematologic or non-hematologic toxicity (assessed in accordance with the CTCAE Version 5.0 criteria).

The following are DLTs:

1. Toxicity causing greater than 2 weeks of dose delay. For example, if a subject has dose delay greater than 2 weeks due to an AE, such AE is a DLT.
2. Grade 4 neutropenia greater than 5 days.
3. ALT/AST $> 3x$ ULN with bilirubin $> 2x$ ULN without another explanation (e.g., cholestasis)
4. Any Grade 3 hypersensitivity reaction is a DLT
5. Grade 4 thrombocytopenia of any duration
6. Grade 3 thrombocytopenia with significant hemorrhage of any duration
7. Febrile neutropenia

And, any non-hematological Grade ≥ 3 toxicities will be a DLT.

The following may be considered as exceptions to DLTs:

1. Grade 3 nausea, vomiting, or diarrhea and Grade 4 vomiting or diarrhea in the absence of maximal medical therapy that resolves in 72 hours
2. Grade 3 fatigue lasting < 5 days
3. Grade 3 hypertension that can be controlled with medical therapy
4. An increase of indirect (unconjugated) bilirubin indicative of Gilbert's syndrome
5. Serum lipase and/or serum amylase CTCAE Grade 3 ≤ 7 consecutive days without clinical signs or symptoms of pancreatitis

5.2.1.1 Definition of DLT Evaluable Population:

Patients enrolled in safety lead-in cohort who receive at least 4 doses and complete the DLT observation period (the first 42 days of induction treatment), unless the patient discontinued the study treatment due to a DLT.

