Hypopituitarism/Hypophysitis (secondary endocrinopathies)	
If secondary thyroid and/or adrenal insufficiency is confirmed (i.e. subnormal serum thyroxine with inappropriately low TSH and/or low serum cortisol with inappropriately low ACTH)
 
 Refer to endocrinologist for dynamic testing as indicated and measurement of other hormones (FSH, LH, GH/IGF-1, PRL, testosterone in men, estrogens in women) Hormone replacement/suppressive therapy as appropriate Perform pituitary MRI and visual field examination as indicated 
If hypophysitis confirmed:
 
 Continue avelumab if mild symptoms with normal MRI. Repeat the MRI in 1 month Withhold avelumab if moderate, severe or life-threatening symptoms of hypophysitis and/or abnormal MRI. Consider 	
Resume avelumab once symptoms and hormone tests improve to Grade ≤ 1 (with or without hormone replacement).
 
In addition, for hypophysitis with abnormal MRI, resume avelumab only once shrinkage of the pituitary gland on MRI/CT scan is documented.
 
Continue hormone replacement/suppression therapy as appropriate.

	
hospitalization. Initiate corticosteroids (1 to 2 mg/kg/day prednisone or equivalent) followed by corticosteroids taper during at least 1 month.
 
 • Add prophylactic antibiotics for opportunistic infections. 	
Other irAEs (not described above)		
Grade of other irAEs (NCI-CTCAE v4)	Initial Management	Follow-up Management
Grade 2 or Grade 3 clinical signs or symptoms suggestive of a potential irAE	Withhold avelumab therapy pending clinical investigation	
If irAE is ruled out, manage as appropriate according to the diagnosis and consider restarting avelumab therapy
 
If irAE is confirmed, treat as Grade 2 or 3 irAE.

Grade 2 irAE or first occurrence of Grade 3 irAE	
Withhold avelumab therapy 1.0 to 2.0 mg/kg/day prednisone or equivalent
 
Add prophylactic antibiotics for opportunistic infections
 
Specialty consult as appropriate
	
If improves to Grade ≤ 1:
 
Taper steroids over at least 1 month and resume avelumab therapy following steroids taper.

Recurrence of same Grade 3 irAEs	
Permanently discontinue avelumab therapy 1.0 to 2.0 mg/kg/day prednisone or equivalent.
 
Add prophylactic antibiotics for opportunistic infections
 
Specialty consult as appropriate
	
If improves to Grade ≤ 1:
 
Taper steroids over at least 1 month.

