6.4.2.2 Toxicity management

Methods to improve patient's symptoms such as use of anticholinergics or antibiotics is allowed at the treating physician's discretion as per usual standard of care. Recommendations for management of Intravesical BCG-specific toxicities are shown in **Table 6**.

Table 6 Intravesical BCG related symptom alleviation and toxicity management

Toxicity	Recommendations
Transient symptoms: urinary frequency, urgency, dysuria, cystitis, malaise, fever < 38.5°C	Expected after intravesical BCG and usually resolves within 48 hrs. Consider symptomatic treatment (anticholinergics, pyridium, acetaminophen). Consider urine culture. Continue intravesical BCG treatment.
Persistent (> 48hr) fever < 38.5°C, cystitis, malaise	Urine culture; hold BCG until symptoms subside.
Fever > 38.5°C for 12-24 h	Urine culture; if culture is negative, consider Isoniazid 300 mg daily for 3 months; May resume intravesical BCG when asymptomatic.

Toxicity	Recommendations
Acute severe illness, local or systemic pneumonitis, hepatitis, prostatitis, ureteral obstruction, renal abscess, persisting high fever > 39°C	Isoniazid 300 mg, rifampin 600 mg and/or ethambutol 1200 mg, daily for 6 months; Discontinue intravesical BCG.
Sepsis	Isoniazid 300 mg, rifampin 600 mg and/or ethambutol 1200 mg daily for 6 months; cycloserine 500 mg twice daily orally; high-dose corticosteroids immediately; Discontinue intravesical BCG.

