8.2.1 Definition of Evaluable Patients for Efficacy Analysis

Evaluable patients will be defined as patients who receive at least 5 doses each of intravesical BCG and avelumab IV during induction treatment (first 8 weeks) and complete the first post-treatment cystoscopy and/or urine cytology for tumor assessment. Patients who discontinued study treatment due to toxicity incurred by previous therapy will be evaluated for safety analysis, but will be replaced by additional patients for the efficacy analysis.

Patients removed from study for early withdraw or hypersensitivity reactions will be replaced if they have received less than 5 doses of study treatment during induction treatment, but will be included in the safety analysis.

Patients who do not receive at least 5 doses of intravesical BCG and avelumab IV during induction treatment will be considered unevaluable for efficacy analysis and will be replaced unless the missed doses were due to development of grade 3-4 adverse events related to study treatment.

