- Overdose of either avelumab, intravesical-BCG or concomitant medication unless the event meets SAE criteria (eg, hospitalization). However, the event should still be captured as a non-serious AE
- Events of progression of the patient’s underlying cancer as well as events clearly related to progression of the patient’s cancer (signs and symptoms of progression) should not be reported as a serious adverse event unless the outcome is fatal within the safety reporting period. If the event has a fatal outcome within the safety reporting period, then the event of Progression of Disease must be recorded as an AE and as a SAE with CTCAE Grade 5 (fatal outcome) indicated.

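### The replacement exception covers only related grade 3-4 events, so related grade 2 immune toxicity and related deaths that cut induction short drop out of the SAP's evaluable set

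*Protocol*

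**What the plan says.** Protocol 8.2.1 makes a patient evaluable for efficacy after at least 5 doses each of BCG and avelumab in the first 8 weeks, plus a first post-treatment cystoscopy and/or cytology. Patients short of 5 doses "will be replaced unless the missed doses were due to development of grade 3-4 adverse events related to study treatment". SAP 5.c repeats the rule.

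Three other sentences also replace patients. Protocol 8.2.1 replaces "Patients who discontinued study treatment due to toxicity incurred by previous therapy" for the efficacy analysis. It also replaces patients removed for early withdrawal or hypersensitivity with fewer than 5 doses, at any grade. Protocol 6.7 replaces every premature discontinuation, with no exception.

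Table 4 of the protocol withholds avelumab below grade 3. For a grade 2 event in its residual (other) category, once improved to grade 1 or less, it says: "Taper steroids over at least 1 month and resume avelumab therapy following steroids taper". The rows for grade 2 pneumonitis and grade 2 to 3 creatinine increase follow the same pattern.

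On analysis sets, protocol 10.2 restricts the statistical analysis to patients as defined in 8.1.1, meaning at least one dose of BCG and avelumab. SAP 5.c assigns its at-least-5-dose population to the quality-of-life analysis and to the measures in SAP Section 8.

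**The concern.** The exception is evidently meant to stop drug-caused failures from being exchanged for patients who tolerate the drug. It does so only for grades 3 and 4. The protocol's own toxicity rules can take a patient below 5 avelumab doses at grade 2, and a fatal event is grade 5.

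If such patients are replaced, the 18 evaluable patients are selected partly on having tolerated treatment. Response, survival-type and completion results from that set would then look better than those of the patients actually treated.

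**Working it through.** **1. The plan's own figure.** Protocol 10.1 gives a lower two-sided 95% Wilson limit of 37.6% for a 60% rate with n = 18. With z = 1.96, z²/n = 0.2134 and z²/(2n) = 0.1067:
- centre = (0.60 + 0.1067)/1.2134 = 0.582
- half-width = 1.96 × √(0.24/18 + 3.8416/(4 × 324))/1.2134 = 0.206
- interval = 37.6% to 78.9%.

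The figure reproduces. It concerns Month 6 completion and makes no allowance for replacement.

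**2. Can a related grade 2 event force fewer than 5 doses?** From protocol 6.3.1 and Table 7, with BCG finishing on schedule, avelumab falls on Days 1, 8, 15, 22, 29 and 36. The week after BCG is skipped, and the next infusions are Days 50 and 64. Eight weeks end on Day 56. Take the shortest plausible hold: onset the day after an infusion, immediate improvement and a 30-day taper.
- After dose 1 (Day 1): resumes from about Day 32. Days 36 and 50 remain, so 1 + 2 = 3 doses.
- After dose 2 (Day 8): resumes from about Day 39. Day 50 remains, so 2 + 1 = 3 doses.
- After dose 3 (Day 15): resumes from about Day 46. Day 50 remains, so 3 + 1 = 4 doses.

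The ±3-day visit window in Table 7 could raise the first two to 4 (using Day 32 or Day 39), still below 5. After dose 4 (Day 22), resumption from about Day 53 misses Day 50 unless that window is used, so I do not rely on that case. After dose 5 the threshold is already met.

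This uses the 8-week limit in 8.2.1. SAP 5.c does not repeat the limit but asks for weekly avelumab. If it were read to admit any infusion in the 12-week cycle (adding Days 64 and 78), the minimum hold would give 5, 5 or 6 doses, and only longer holds would fall short.

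**3. Related death.** The protocol uses "CTCAE Grade 5 (fatal outcome) indicated" for fatal outcomes. That sentence (9.2.1) concerns fatal cancer progression, but it shows the scale in use. A related death before dose 5 is, read literally, outside grade 3-4 and is replaced. SAP 8.d to 8.g count death against the patient in PFS, OS, RFS and CFS, yet this death would not be in the set. SAP 8.e also leaves OS unreported if there are no deaths.

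**4. Where the exclusion acts.** Under protocol 10.2, a replaced patient who received both drugs stays in the denominator. Under SAP 5.c, that patient leaves all of SAP Section 8, and 8.a of that section is the induction completion rate.

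**5. Size.** The documents give no rate for these events, so the number replaced, k, is an assumption. Its outer limit is 27 − 18 = 9, from the enrolment cap in 10.3. Other assumptions: no other non-completers, 9 complete responses among the 18, and no response in any replaced patient (the worst case for CR).

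| k | Completion, SAP set | Completion, all treated (95% Wilson) | CR, SAP set | CR, worst case |
|---|---|---|---|---|
| 1 | 18/18 = 100% | 18/19 = 94.7% (75.4–99.1) | 50% | 9/19 = 47.4% |
| 2 | 100% | 18/20 = 90.0% (69.9–97.2) | 50% | 9/20 = 45.0% |
| 4 | 100% | 18/22 = 81.8% (61.5–92.7) | 50% | 9/22 = 40.9% |
| 9 | 100% | 18/27 = 66.7% (47.8–81.4) | 50% | 9/27 = 33.3% |

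If 2 related grade 3-4 non-completers are kept and 2 others replaced, completion reads 16/18 = 88.9% instead of 16/20 = 80.0%.

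**The case against.** **What stands against the point.** Protocol 10.2 keeps these patients in the analysis, and they stay in the safety set under both documents. SAP 5.a also assigns compliance analyses to the at-least-one-dose population, and induction completion could be called compliance. A fatal event first recorded as grade 4 might arguably meet the exception. The trial tests no hypothesis, and 9/18 already has a Wilson interval of about 29% to 71%. All of this limits the size and certainty of the bias. It does not remove the gap, because SAP 5.c names Section 8 without excepting 8.a.

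**Stronger readings that a reader might infer, and that the documents do not support:**
- *Lead-in dose decisions are corrupted.* "Toxicity causing greater than 2 weeks of dose delay" is a DLT with no grade requirement, but the DLT population is defined separately in 5.2.1 and retains patients who discontinue because of a DLT. Replacement for efficacy does not enter that decision.
- *Low-grade BCG symptoms lead to replacement too.* Table 6 says "Urine culture; hold BCG until symptoms subside" for persistent low fever, cystitis or malaise. But eight weeks offer eight weekly slots for five required doses, and 6.4.2.1 has a postponed instillation resume the following week. A shortfall by this route is not shown.
- *On-study BCG toxicity will be blamed on earlier BCG.* Every patient has had BCG, and the previous-therapy sentence has no attribution rule. But 9.4 rates an event as possibly related even when other therapies could have produced it. Misattribution is speculation.
- *The protocol contradicts itself by calling these patients failures.* Section 1.2 says "Patients who cannot tolerate 5 of 6 weekly treatments as part of induction therapy will be considered treatment failures", but that concerns the primary endpoint, and the similar note in 6.4 counts BCG doses only. A patient can fail completion and separately be unevaluable for efficacy.
- *Every replaced patient is a non-responder.* Protocol 6.4 lets BCG continue while avelumab is held, and 6.9 follows early discontinuers for response. Some may have an observed CR.

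**Conclusion.** The point holds as a gap in the SAP's evaluable set. Related grade 2 immune events that force a long avelumab hold after doses 1 to 3, and related deaths before dose 5, are replaced under the wording of 8.2.1 and SAP 5.c. Where the SAP is followed, results shift in the favourable direction. Where protocol 10.2 is followed, these patients stay in, so the two documents must be reconciled.

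With 2 such patients and no other non-completers, induction completion is overstated by 10 percentage points and CR by at most 5. Both figures rest on assumed counts, and the CR figure also on no response in either patient. The dose count rests on the 8-week limit, BCG finishing on schedule and a taper of 30 days or more. The change should be made before analysis; nothing here questions the lead-in decision rules.

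**What to change.** 1. In protocol 8.2.1 and SAP 5.c, widen the exception to missed doses due to any adverse event at least possibly related to avelumab or BCG, of any grade including grade 5, or to a DLT. State the 8-week limit in SAP 5.c as well.
2. Keep these patients in the efficacy analysis with their observed response. Waive the first-assessment requirement for them: count those with no assessment as non-responders, and deaths as events.
3. Calculate induction completion in the at-least-one-dose set, with all of these patients as non-completers, and say so in SAP 8.a.
4. Reconcile the replacement wording in 6.7, the hypersensitivity and previous-therapy sentences in 8.2.1, and the analysis sets in 10.2 and SAP 5.c, so that none removes a related-toxicity failure from analysis.

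The changes concern analysis sets only, not patient care. They touch several sentences across the two documents. Fewer patients are replaced, so no extra patients are needed. The cost is that reported rates may be a few points lower.

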9 SAFETY MONITORING AND REPORTING PROCEDURES

The safety plan for patients in this study is based on clinical experience with IV avelumab and intravesical-BCG in completed and ongoing studies. The anticipated important safety risks are outlined in [sections 6.4.1](#) and [6.4.2](#).

Measures will be taken to ensure the safety of patients participating in this study, including the use of stringent inclusion and exclusion criteria and close monitoring of patients during the study. Administration of avelumab will be performed in a monitored setting in which there is immediate access to trained personnel and adequate equipment and medicine to manage potentially serious reactions. After initiation of study treatment, all adverse events will be reported until 90 days for avelumab after the last dose of study treatment or until initiation of new systemic anti-cancer therapy, whichever occurs first. Serious adverse events and adverse events of special interest will continue to be reported until 90 days for avelumab after the last dose of study treatment or until initiation of new systemic anti-cancer therapy, whichever occurs first. Guidelines for managing anticipated adverse events, including criteria for dosage modification and treatment interruption or discontinuation, is provided in [section 6.4](#).

Safety assessments will consist of monitoring and reporting adverse events and serious adverse events per protocol. This includes all events of death and any study-specific issue of concern.

9.1 Adverse Event Reporting Period

The study period during which all AEs and SAEs must be reported begins after informed consent is obtained and initiation of study treatment and ends 90 days following the last administration of study treatment or study discontinuation/termination, whichever is earlier. After this period, investigators should only report SAEs that are attributed to prior study treatment. Stopping rules for toxicity are defined in Tables 2-4 & 6.

The principal investigator is responsible for ensuring that all AEs and SAEs that are observed or reported during the study, are collected and reported to the FDA and appropriate IRB in accordance with CFR 312.32 (IND Safety Reports).

All reportable events should be sent to the Sponsor via email:

[contact]

OR

Fax at [name].

In addition, the principal investigator is responsible for notifying EMD Serono GPS in parallel of such events within 2 business days or 3 calendar days (whichever comes first) of the Sponsor/PI becoming aware of the event (ideally using the applicable safety report form provided by EMD). The following reportable events must be submitted to EMD Serono:

- Serious Adverse Events
- Exposure during Pregnancy or Breastfeeding (even if not associated with an adverse event)
- Occupational exposure (even if not associated with an adverse event)
- Potential drug-induced liver injury (Hy's Law cases): These events are considered important medical events and should be reported as SAEs.
- Contact information for submission of reportable events to EMD Serono:

[contact]

OR

E-mail: [contact]

Post-Study Adverse Events: The principal investigator should expeditiously report any SAE occurring after a subject has completed or discontinued study participation if attributed to prior avelumab and/or intravesical-BCG exposure. If the investigator should become aware of the development of cancer or a congenital anomaly in a subsequently conceived offspring of a female subject who participated in the study, this should be reported as an SAE.

9.1.1 Reporting Suspected Unexpected Serious Adverse Reactions

In compliance with FDA regulations, as contained in 21 CFR 312.32, all Suspected Unexpected Serious Adverse Reactions (SUSARs) must be reported by Stephenson Cancer Center, University of Oklahoma Health Sciences Center (the sponsor for this study) to the FDA within the required timeframes. Research staff should notify the PI within 24 hours of awareness of an SAE for timely evaluation of reportability to FDA.

The Sponsor/PI or designee is responsible for notifying EMD Serono Drug Safety within 2 business days or 3 calendar days (whichever comes first) of awareness.

Contact information for submission of reportable events to EMD Serono:

[contact]

OR

E-mail: [contact]

Specifying:

PROTOCOL Number and/or Title

EMD Serono assigned Study Number

SUBJECT Number

SITE Number/PI Name

SAE/ONSET DATE

With the assistance of Stephenson Cancer Center Clinical Trial Office (SCC CTO), all SUSARs must be reported to the FDA by the investigator within 7 (serious criteria of death or life threatening) or 15 (all other seriousness criteria) calendar days of awareness.

Supporting and follow up data: Any supporting or follow up documentation must be submitted to the regulatory authorities per federal regulations and institutional standards when available. The Sponsor/PI or designee is also responsible for notifying EMD Serono Drug Safety about the supporting or follow up data.

9.1.2 MedWatch 3500A Reporting Guidelines

In addition to completing appropriate patient demographic and suspect medication information, the report should include the following information within the Event Description (section 5) of the MedWatch 3500A form:

1. Treatment regimen
2. Protocol description (and number, if assigned)
3. Description of event, severity, treatment, and outcome if known
4. Supportive laboratory results and diagnostics
5. Investigator's assessment of the relationship of the adverse event to each investigational product and suspect medication

MedWatch 3500A (Mandatory Reporting) form is available at

<http://www.fda.gov/medwatch/getforms.html>

Follow-up Information:

Additional information may be added to a previously submitted report by any of the following methods:

1. Adding to the original MedWatch 3500A report and submitting it as follow-up
2. Adding supplemental summary information and submitting it as follow-up with the original MedWatch 3500A form
3. Summarizing new information and faxing it with a cover letter including patient identifiers (i.e., D.O.B. initial, patient number), protocol description and number, if assigned, brief adverse event description, and notation that additional or follow-up information is being submitted (The patient identifiers are important so that the new information is added to the correct initial report)

Occasionally EMD Serono, may contact the sponsor/principal investigator for additional information, clarification, or current status of the patient for whom an adverse event was reported. For questions regarding SAE reporting, you may contact SCC CTO study's regulatory project manager at [contact].

